## **Background:**

Venous thromboembolism (VTE) is a major public health problem with over 500,000 incident or recurrent VTE events occur in the US annually. Survival after VTE is reduced, especially after pulmonary embolism (PE). The incidence of VTE in Olmsted County, MN increased by ~5% per decade over the 30-year period, 1981-2010. Anticoagulation for VTE has been the mainstay treatment with little advancement. Unfortunately, acute and chronic venous disorders are extremely common in those that experience VTE. Post-thrombotic syndrome (PTS) is one of the dreaded long-term complications of deep venous thrombosis (DVT). It's been estimated that 1 to 3 of 1000 people in general population is affected by DVT and 25% to 50% patients of patients with DVT develop PTS. The manifestations of PTS can vary from minor leg swelling at the end of the day to severe complications of debilitating limb pain, intractable edema, and leg ulcerations requiring extensive nursing and medical care. It can reduce the patient's quality of life in addition to being a significant financial burden. It is estimated that annually we spend over a billion dollars (up to 2% of the total healthcare budget in all Western countries) on the treatment of chronic wounds. There are still huge gaps in understanding the underlying mechanism and progression of the condition.

Expedient resolution of thrombosis may have a significant impact on PTS. Resolution and recanalization of venous thrombosis generally begins within 1 week of the acute episode. Studies have shown that at least 5% of thrombosed venous segments completely clear within 1 week and 16% to 51% of the cases

resolved within 6 months. Killewich et al demonstrated thrombus regression was evident at 1 to 2 weeks and progressed such that only 26% of residual thrombus remained at 24 to 36 weeks. Complete resolution of thrombus occurred in 10 of 18 patients (56%) who completed the 9-month study.

O'Shaunessy et al reported that 60% of their patients had completely resolved their thrombus by the end of 1 year. This study examined 63 above-knee DVT anatomic segments with duplex scanning at 1 week, 1 month, 6 months, and 1 year after the acute event. The segments under investigation were the external iliac vein (EIV), common femoral vein (CFV), superficial femoral vein (SFV), and popliteal vein (PV). Initially, a greater number of segments were occluded (71%) than partially thrombosed (29%). The occluded segments were predominantly in the SFV and PV. At 1 year the thrombi had fully resolved in 60% of the venous segments, 27% remained partially recanalized, and 13% were occluded. At 1-year follow-up the thrombus had fully resolved in 103 segments: 94% of the EIVs, 78% of the CFVs, 42% of the SFVs, and 54% of the PVs. Of these, 61% of the segments were found to be competent without reflux flow, and 39% were incompetent with reflux flow of greater than 1 second. The time involved for individual segments to fully recanalize varied from 1 week to 1 year. Segments that resolved within the first 6 months had a higher frequency of valvular competency than incompetency ( $P > .006$ ). The segments that resolved after 6 months had a higher incidence of incompetency to competency (31:13), but this was not statistically significant. The SFV and PV had a higher incidence of valvular incompetence than the EIV and CFV. All venous segments that were partially recanalized at 1 year were found to have significant reflux. The SFV had the highest incidence of total occlusion at the end of 1 year (36%). Many of the occluded SFVs had established collateral pathways that displayed no evidence of reflux. Ramshorst et al. observed thrombosis resolution to occur in the first 1 to 3 weeks after acute DVT and appeared to occur at an almost exponential rate. They noted that recanalization occurred mainly in the first 6 weeks after diagnosis, but clot resolution eventually occurred in 75% of the thrombosed segments within 6 months. Caprini et al. reported that complete resolution had occurred in more than 40% of thrombosed venous segments within 3 months after the diagnosis of DVT, and lysis had occurred in more than 70% of segments within 6 months of treatment.

To further reduce the VTE burden, better treatments are needed to resolve VTE other than anticoagulation alone. The largest randomized trial to date is the Pulmonary Embolism International Thrombolysis (PEITHO) trial, and resulted in 1,006 patients with acute sub-massive PE-defined as echo evidence of RV dysfunction or positive troponin-to receive anticoagulation with heparin plus tenecteplase or placebo. There was significantly (2.6% vs. 5.6%;  $P=0.015$ ) lower death or hemodynamic collapse within 7 days and increased rates of intracranial hemorrhage (2.4% vs 0.2%;  $P=0.003$ ) and major bleeding in the thrombolytic group. The Seattle II study was a prospective, single-arm multicenter trial of ultrasound facilitated, low-dose fibrinolysis for acute massive and sub-massive PE. There was a 25% decrease in CT-measured RV/LV ratio over 48 hours, 0% intracranial bleeding, 2% in-hospital death, and 2.7% 30 day mortality due to catheter-directed low-dose fibrinolysis. The rationale for the Seattle II study was to use catheter-directed-low dose fibrinolysis as a disruption device to help dissolve clot. However, there is limited data on the use of vascular boot and warming plus standard anticoagulation in the long term management of patients with DVT and/or PE and its effect on the development of PTS. Warming of the lower extremity enhances blood flow in the treatment of superficial vein thrombosis.

Currently the standard method for diagnosing and evaluating DVT is by 2-D ultrasound with compression and visualization of the vein. Due to the lack of accurate age determination method of DVT, about 30% of DVTs are wrongly staged by using common diagnostic modalities and therefore this leads to therapeutic dilemmas. As thrombus undergoes a stiffening process, the elasticity of the thrombus may serve as a predictor

for the staging of blood clots. Ultrasound elastography is a noninvasive technique to measure tissue stiffness and is a potential technique to determine the age of DVT. When DVT changes due to resolution the function and viscoelastic properties also change. We propose the use of a quantitative, noninvasive method call Shear wave Dispersion ultrasound vibrometry, to measure the viscoelastic properties of the vein.

Instead of studying compressional waves propagation in the MHz range, other approaches to study the mechanical properties of soft tissues have used shear waves at low frequencies (typically ranging from 50 Hz to 1000 Hz) (Muthupillai et al. 1995; Sarvazyan et al. 1998). Gennisson et al. in 2006 and Schmitt et al. in 2011 used mechanical vibrators to generate shear waves in the blood samples, allowing the study of the dynamic process of blood coagulation (Gennisson et al. 2006) and the comparison of different rheological models (Schmitt et al. 2011). Another approach using radiation force was described by Viola et al. in 2010 in which they used the ultrasound push to move the blood clot and measured the displacement generated. This technique was used to measure the change in relative compliance of ex vivo clots as they were formed (Viola et al. 2010). Even though it has been shown that the composition of blood clots is not homogenous (Taber et al. 1996), to our knowledge there are no studies describing the elastic properties of blood clots.

Therefore, there is a real interest in a noninvasive technique for the study of two-dimensional (2-D) elasticity properties of blood clots. This technique could be used to diagnose the age of thrombi, stratify the resolution of blood clots and help understand the coagulation process from a mechanical standpoint. It could also potentially be used to monitor the effect of therapies that are currently used on the clot elasticity.

### **Study Rationale Innovation and significance:**

Warming of the lower extremity enhances blood flow in the treatment of superficial vein thrombosis and has been well established. However, the effect of vascular boot warming plus standard anticoagulation on deep venous disease progression is unknown and may prove to reduce DVT with standard anticoagulation more effectively and quicker with reduced risk for PTS. To date, there is no randomized control study evaluating the effect of vascular boot warming plus standard anticoagulation in venous insufficiency. We hypothesize that the combination of vascular boot warming and standard anticoagulation will result in improvement in calf muscle pump function, thus improvement in venous physiology and quicker resolution of DVT and associated clinical symptomatology of post thrombotic syndrome. Ultrasonography with shear wave elastography imaging is a novel ultrasound technology that potentially can quantify and assess thrombosis age, evolution of thrombosis, and risk of detachment. These evaluations can be readily performed in the patient's examination room on a single ultrasound system. The overall anticipated results of our research proposal are to demonstrate that: 1) DVT may resolve more effectively with a vascular boot through warming evaluated by standard 2-D ultrasonography with compression (standard therapy); 2) shear wave elastography is a feasible diagnostic tool in those with lower extremity thrombosis; 3) shear wave elastography can provide a more accurate and reliable method to assess the age of thrombosis and better quantification of thrombosis resolution while assessing the natural history, progression, and risk of detachment; 4) this technology can readily be incorporated into the daily workflow to improve diagnostic and prognostic value for detection of DVT and resolution [It has been estimated that the average image acquisition time to be added to a standard ultrasound study is minimal (7-10 minutes for shear wave elastography imaging) 5) these techniques can improve prediction of complications among those with DVT and; 6) these techniques can help decrease the number of age indeterminate thrombus that may result in unnecessary treatment with anticoagulation and its associated risks.

**Subject Information** – charts, records, images, or specimens are considered ‘subjects’

*Target accrual is the proposed number of subjects to be included in your study at your site. “Subjects” may include Mayo Clinic charts, records, or specimens, **and/or** charts, records, or specimens received at Mayo Clinic from external sources for collaborating analysis by the investigator under this IRB application:*

**Target accrual:** 30 patients (15 patients with vascular boot vs 15 patients without vascular boot)

**Subject population:**

All patients diagnosed with acute lower extremity DVT per ultrasound ± pulmonary embolism (PE) per computed tomography scan seen in the Thrombophilia clinic or Mayo Hospital for start of anticoagulation will be approached for participation in the study.

**Inclusion Criteria**

1. Age ≥18
2. Able to tolerate wearing a vascular boot, if randomized to this group.
3. Diagnosis of acute DVT±PE (within 24 - 48 hours) and received approximately 24 hours of anticoagulation prior to starting the study.

**Exclusion Criteria**

1. Unable to tolerate wearing a vascular boot
2. Unable to comply with keeping log of activity/ of wearing a vascular boot.
3. Weight > 300 pounds. (*weight limit for the venous plethysmography chair*)
4. Previous history of DVT or PE.
5. On anticoagulation for another purpose (example stroke prevention with atrial fibrillation).
6. Patients who do not accept to participate in research studies.
7. Pregnant women will not be allowed to participate
8. Patients less than 18 yrs

Yes  No Will a Certificate of Confidentiality (COC) be obtained from NIH?

## Study Design

### Methods

Patients with diagnosis of acute lower extremity DVT (proximal and distal) and/or pulmonary embolism will be identified and approached for participation, when they are seen in the Thrombophilia Clinic or Mayo Hospital for management of the acute VTE. If they match the preset inclusion and exclusion criteria, they would then be consented during this visit and scheduled for baseline studies at a later date.

#### Baseline studies will include:

- (1) Venous plethysmography: (ejection fraction, VFR, PDR T90, EDV T90, MV, F1.0).
- (2) Lower Extremity Ultrasound: DVT (thrombus) evaluation with 2-D ultrasonography (standard) and shear wave elastography (done within 1 day of baseline clinical ultrasonography).
- (3) Other relevant clinical information (such as height, weight, BMI, bilateral calf circumference, edema, leg pain, ulcerations, previous LE surgery, use of compression stockings, and any current set exercise program). Demographical data, common vascular risk factors (including tobacco use, coronary and peripheral arterial occlusive disease, diabetes, hypercholesterolemia, and hypertension) and the treatment information, will be obtained from chart review via ACE database and Synthesis. All data will be entered and stored in RedCap research tool.
- (4) Anatomic distribution of thrombi at initial examination will be documented as single segment and/or multi-segment(s) involved. The segments will be label as: external iliac vein (EIV), only if clot extends above the common femoral vein; common femoral vein (CFV); femoral vein (FV) (upper, middle, lower); deep femoral vein (DFV); popliteal vein (PV); posterior tibial vein (PTV); gastrocnemius (G-calf); peroneal vein-calf (PV-calf); soleal vein-calf (SV-calf) (see Table 1).

Table 1.0

Site	Anatomic Distribution of Thrombi			
	Initial	3 days	10 days	3 months
Single Segments				
External Iliac (EIV); if evaluated				
Common femoral (CFV)				
Femoral- Upper (FV)				
Femoral - Middle				

Femoral - Lower				
Deep Femoral (DFV)				
Popliteal (PV)				
Posterior Tibial (PT-calf)				
Gastrocnemius (G-calf)				
Peroneal (P-calf)				
Soleal (S-calf)				
Total				
Multisegment				
EIV- CFV				
EIV- CFV-FV				
EIV- CFV-FV-PV				
EIV- CFV-FV-PV-calf				
CFV-FV				
CFV-FV-PV				
CFV-FV-PV-calf				
FV-PV				
FV-PV-calf				
Total				

Patient will then be randomized to vascular boot plus standard anticoagulation program or standard anticoagulation using the randomizer built into RedCap.

**Standard of Care (SOC) Group (no vascular boot utilized)**: Patients will receive standard anticoagulation (determined at discretion of the treating provider), baseline studies, and follow up at the end of treatment (3months).

**Vascular Boot (VB) Group (includes vascular boot in addition to SOC)**: Patients will receive standard anticoagulation (determined at discretion of the treating provider), baseline studies and standardized vascular boot warming (see below). All patients randomized to this group will wear the vascular boot for a minimum of 30 minutes per day for the first 10 days of participation. Patients in this group may initially be enrolled at either the thrombophilia clinic or the hospital.

**Standardization of the vascular boot warming:**

The vascular boot is designed to completely surround the foot, heel and calf, insulating the limb. For each vascular boot session, the following data will be recorded:

- (1) Total duration of wearing vascular boot during first 10 days of study participation
- (2) Affected leg pain measured on a 0-10 scale at initial vascular boot warming (baseline) and every day during the calf warming while participating in the study.

**Follow up data (SOC and VB Groups) include:**

- (1) Ultrasound of the leg with DVT and leg circumference measurement at 3 days, 10 days, and 3 months. Ultrasound data will include data on thrombus resolution, such as size and recanalization present.
- (2) Venous plethysmography at 3 months.
- (3) Study Questionnaires:
  - a. Godin questionnaire (validated questionnaires to measure physical activity)
  - b. VEINES-QOL (generic physical quality of life questionnaire)
  - c. Villalta Score (to assess Post-Thrombotic Syndrome)

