**Study Procedure**

All subjects included in this study will have a diagnosis of deep vein thrombosis that will undergo standard anticoagulation with or without wearing a vascular boot. Medical charts will be abstracted for clinical, laboratory, medications, imaging and pathologic findings. Subjects will undergo their initial (baseline) clinically indicated DVT ultrasound for diagnosis of lower extremity DVT. The second clinically indicated limited venous ultrasound will be completed on post-DVT day 90 (14±days) to evaluate resolution. Research ultrasound intervals will then occur on days 0 (+1 days), 3 (-2/+5 days), 10 (±5 days), and 90 (14±days). Shear wave elastography will be conducted at all post-treatment ultrasound intervals. We will compare the shear wave elastography to the opposite lower extremity veins on the same individual for a control if DVT is not present in that extremity at that time or previously.

Commercially available ultrasound systems (Logiq E9, GE Medical Systems, Milwaukee, WI, USA) equipped with phased-array and linear transducers will be utilized. Longitudinal and short axis images of each clot will be acquired and digitally stored for offline analysis. The short axis images will be acquired. 2-D images, 2D shear wave and elastography images will be acquired and digitally stored for off-line analysis. All measurements will be made in a blinded fashion by a single observer.

**Shear Wave Elastography:** The subject will be asked to lay on a hospital bed for ultrasound imaging. The veins of the lower extremity will be visualized using ultrasound imaging, and the depth of the venous wall will be noted. The focal depth on the device will be set to measure shear wave propagation in the walls of the vein and in the thrombus. Measurements will be made at multiple locations along the veins length.

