## **Endpoints**

### **Primary:**

Early resolution of the DVT±PE as measured by the ultrasound. Partial recanalization will be defined by normal or diminished flow with distal augmentation and partial incompressibility of the vein (>50% or <50%). Complete recanalization will be defined by spontaneous phasic flow and a completely compressible vein.

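### The day-3 and nominal day-10 scans fall in the boot-wearing period with no fixed or recorded boot-to-scan interval, so recent warming could shift the flow part of intermediate ultrasound grades in the boot arm only

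*Combined protocol and SAP*

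**What the plan says.** **Exposure.** In Methods, boot-arm patients "will wear the vascular boot for a minimum of 30 minutes per day for the first 10 days of participation". No time of day and no upper limit are given. The comparator is headed "Standard of Care (SOC) Group (no vascular boot utilized").

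**Scans.** Follow up data, item 1, lists "Ultrasound of the leg with DVT and leg circumference measurement at 3 days, 10 days, and 3 months" for both groups. Study Procedure adds the windows: "Research ultrasound intervals will then occur on days 0 (+1 days), 3 (-2/+5 days), 10 (±5 days), and 90 (14±days").

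**What is logged.** Standardization of the vascular boot warming asks for "Total duration of wearing vascular boot during first 10 days of study participation" and a daily pain score. It does not ask for session start or stop times.

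**Premise.** Study Rationale states: "Warming of the lower extremity enhances blood flow in the treatment of superficial vein thrombosis and has been well established".

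**Grading.** Flow enters the ultrasound definitions in Ultrasound Measurements and Criteria and again under Endpoints, Primary. For example: "Complete recanalization will be defined by spontaneous phasic flow and a completely compressible vein".

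No section sets a rest period, a temperature-equilibration period or an interval between a boot session and a scan.

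**The concern.** The primary endpoint is early resolution on ultrasound, and days 3 and 10 are the early scans. In the boot arm they are taken mostly while the boot is still in daily use. A patient could come to the scan straight from a session, or a day after the last one, and the data would not show which. If warming raises flow for some time afterwards, the boot arm's flow findings mix two things: clot change, which the trial wants to measure, and the immediate effect of a warm leg, which it does not. The control arm has no such exposure, so randomization does not balance the effect. Because the interval is not recorded, analysis cannot remove it later.

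**Working it through.** **1. Overlap of scan windows and boot days.** Assume boot days and scan days are counted from the same start, with boot days 1 to 10.

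- Day 3: 3 − 2 = 1 to 3 + 5 = 8, which is 8 allowed days. All 8 are boot days.
- Day 10: 10 − 5 = 5 to 10 + 5 = 15, which is 11 allowed days. Days 5 to 10 are boot days, so 6 of 11; days 11 to 15 (5 of 11) come after the required period. If the boot period is counted as days 0 to 9, the overlap is 5 of 11 and day 10 is the first day after it.
- Day 90: 90 − 10 = 80 days after the boot period. Reading the window as 14 days either side, the earliest scan is day 76, which is 66 days after it.

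**2. Can the interval be recovered?** The listed boot data are total duration and pain. Exclusion Criteria mentions a log of boot wear but does not say what it holds. On the data listed, the interval cannot be recovered.

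**3. Which grades can flow move?** From Ultrasound Measurements and Criteria:

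- Occlusive: no flow on augmentation, and an incompressible vein.
- Partial: normal or reduced flow on augmentation, and a partly incompressible vein, split at 50%.
- Complete: spontaneous phasic flow, a fully compressible vein and no residual clot. Endpoints leaves out the last element but keeps compressibility.
- Near occlusive: a column in Table 2.0 with no definition.

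Flow alone never gives a complete grade. But a vein in which flow has become detectable and which is still incompressible is neither occlusive (flow is present) nor partial (it is not partly compressible). The reader must choose a column. The 50% split is a second soft border: in Ultrasound Measurements the percentages stand next to flow, and under Endpoints they follow compressibility. If the split is read as flow, a rise from reduced to normal could cross it; if it is read as compressibility, it could not.

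**4. Size.** The documents give none. One patient in an arm is 1/15 = 6.7 percentage points, but only if a patient-level responder rule exists. Endpoints states none, and Table 2.0 grades up to 11 sites per leg.

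For scale only, suppose such a rule, no true effect, a true rate p in both arms, and a share m of boot-arm non-responders graded as responders. The boot arm's observed rate is then p + (1 − p)m. For p = 16% and m = 10%, this is 0.16 + 0.84 × 0.10 = 24.4%. Exact enumeration with 15 per arm at two-sided 0.05 gives these chances of a false-positive result, by uncorrected chi-square (Fisher's test in brackets):

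| Assumed p | m = 0 | m = 10% | m = 20% | m = 30% |
|---|---|---|---|---|
| 5% | 0.5% (0.1%) | 8.1% (2.6%) | 28.6% (14.8%) | 53.9% (35.9%) |
| 16% | 4.3% (1.4%) | 8.7% (3.5%) | 19.5% (9.2%) | 35.1% (19.1%) |
| 40% | 4.9% (1.6%) | 5.9% (2.2%) | 9.4% (4.1%) | 15.6% (7.8%) |

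Both p and m are assumptions. The table shows how the result would respond to misgrading; it does not estimate how much will occur.

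**The case against.** The strongest reply is that the grades do not rest on flow alone. Each flow-based grade also needs a compressibility finding, flow is judged on augmentation for the occlusive and partial grades, and partial accepts both normal and reduced flow. A reader might infer that warming could produce false complete recanalization. The definitions do not support that. This part of the objection stands and confines the point to the intermediate borders.

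The premise is also thin. The sentence on warming concerns superficial vein thrombosis, the next one says the effect on deep venous disease is unknown, and the reference attached to it is listed as a trial of supervised exercise against stenting in claudication. Nothing says how large the flow change is or how long it lasts. This stands too: an effect at the time of the scan is an assumption. It remains the protocol's own stated mechanism, so the plan should guard against it.

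A reader might also infer that a warm leg unblinds the assessment. Study Procedure has images stored and read off-line by one blinded observer, so unblinding of the measurements is not shown. Blinding does not settle the timing question, however, because a blinded reader still records flow that was really present when the image was taken.

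Finally, this is a 30-patient pilot. That lowers the stakes, but Statistical Considerations still plans tests at 0.05, and the remedy costs very little.

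**Conclusion.** The point holds as a gap in measurement timing. All allowed day-3 scan days, and 6 of 11 allowed day-10 scan days (5 of 11 on the other count), lie in the boot period. The boot-to-scan interval is neither fixed nor recorded, and flow is part of the grading. Recent warming could shift the flow component in the boot arm only, at the borders between occlusive, near occlusive, under 50% and over 50%.

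Three stronger readings are not supported. Not every day-10 scan falls during boot use. A demonstrated bias in favour of the boot cannot be claimed, because the size, duration and presence of the effect at the scan are unknown. The 6.7-point figure is not an effect size, because no responder rule is stated. An acute effect on leg circumference is likewise not documented, and circumference is not a listed endpoint. Day 90 is unaffected. This is a cheap improvement to an early measurement, not a flaw that invalidates the trial.

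**What to change.** In Follow up data, item 1, and in Study Procedure, add that at the day-3 and day-10 visits the ultrasound, elastography and leg circumference are done before that day's boot session, after the same resting condition in both arms. Add one field to the scan form for the date and time the boot was last worn, and keep that field from the observer who makes the blinded measurements, since it would reveal the arm. Elastography and circumference are included because they are taken at the same visits.

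This sets when measurements are taken. It does not restrict boot use, and the daily minimum is unchanged. The cost is one scheduling sentence and one form field. The small downside is that on scan days the appointment must be timed ahead of the session.
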